This controlled not-randomized pilot study with repeated measures was conducted at the Touro University Nevada College of Osteopathic Medicine. Healthy 21-35 years old students and employees volunteered in the study. The experimental group received the three cranial osteopathic manipulative techniques, namely, occipital-atlantal decompression, occipital-mastoid decompression, and compression of the fourth ventricle, consecutively applied. This study included two control groups; one group received sham manipulations, and the second group did not receive any manipulations and was the non-touch group.

The computerized MP150 BIOPAC System was used for data collection and analysis. The skin electrodes were used for the one-lead ECG and impedance cardiography. Digital data were recorded during the entire experimental protocol. The blood pressure was measured manually before and after the experimental procedure using blood pressure cuff and stethoscope. Cardiovascular responses to OMT were evaluated by using the heart rate variability test (HRV), calculating changes in cardiac contractility, and comparing changes in pre- and post- blood pressure readings.

An analysis of variance (ANOVA) with a Bonferroni post-hoc test was used to evaluate treatment effects. The type I error rate (alpha) was set at 0.05.

Detailed Description: Healthy, 21-35 years old, male and female volunteers were recruited from Touro University students, faculty and staff using a brochure, poster, e-mail and personal conversation. Each participant signed an informed consent form. Participants were allowed to participate in multiple experiments (in the experimental and control groups) at least 7 days after the last experiment.

Each subject's weight and height were measured before the procedure. Anthropometric measures were used in cardiac impedance analysis, and as descriptive statistics of the studied population. All cardiovascular parameters were recorded by using a non-invasive method. We used disposable skin electrodes for impedance cardiography and a one-lead ECG.

The subjects were lying in the supine position and were asked to relax. All surface electrodes were connected to the computerized MP150 BIOPAC System for data recording. The duration of experimental protocol was about 30 minutes, and included three intervals: 10 minutes, pre-OMT rest phase (Rest); 8 to 12 minutes (about 10 minutes) of the OMT/Sham (Manipulations); and 10 minutes post-OMT recovery phase (Recovery).

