Data analysis: Most cardiovascular response variables were measured at baseline, immediately after manipulation ("immediate response"), and at the end of protocol ("after rest"). The immediate responses and at the end of protocol were calculated on a percentage basis relative to baseline to control some individual variations.

The percent response variables were each analyzed in a three-way analysis of variance (ANOVA) which included time ("Immediate response", "after rest"), treatment (cranial manipulation, sham), and sex (male, female) as fixed effects. For significant interactions in the ANOVA, a Bonferroni post-hoc test was used to compare treatment effects within time, sex, or both. The type I error rate (alpha) was set at 0.05. The relationships among dependent variables were described with Spearman correlations between percent response variables within. Analyses were done in Rv3.5.1 (R Core Team 2018).

Conditions

Conditions: Healthy Young Adults

Keywords: Osteopathic manipulations,
autonomic,
cardiovascular

Study Design

Study Type: Interventional

Primary Purpose: Basic Science

Study Phase: N/A

Interventional Study Model: Parallel Assignment

Number of Arms: 3

Masking: None (Open Label)

Allocation: Non-Randomized

Enrollment: 51 [Actual]

Arms and Interventions

Arms	Assigned Interventions

Experimental: Cranial OMT The experimental group received the three cranial osteopathic manipulative techniques, occipital-atlantal decompression (OAD), occipital-mastoid decompression (OMD), and compression of the fourth ventricle (CV4), consecutively applied.
	
Procedure/Surgery: Cranial manipulation group, or cranial osteopathic techniques (OMM) Cranial OMT procedure: Subjects were relaxed lying on the back for entire time of the research protocol (approximately 30 min). Osteopathic physician performed the osteopathic manipulations using his hands. The physician gently applied a small amount of force to the neck and head to release tissue tension until feeling a softening and warmth of tissues. Subjects experienced a sensation of slight pulling, releasing, or relaxing of the tissue.
 
Other Names:
 
• Cranial osteopathic manipulations, cranial osteopathic techniques, cranial OMT procedure

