
Sham Comparator: Sham manipulation The osteopathic physician placed his hands on the skull of the subject but did not influence cranial motion.
	
Procedure/Surgery: Sham manipulation The osteopathic physician placed his hands on the skull of the subject but did not influence cranial motion.
 
Other Names:
 
• Sham

No Intervention: Non touch group The control group whose members did not receive any manipulations.
	

Outcome Measures

Primary Outcome Measure:

1. Heart rate variability

The heart rate variability test was used to study the effect of OMT on heart rate and, by inference, on autonomic nervous system activity. A decrease in heart rate accompanied by an increase in vagal and decrease in sympathetic activity would indicate parasympathetic activation by OMT.

[Time Frame: The responses were measured immediately after the physician finished OMT/Sham (after Manipulations phase) and 10 minutes after post-OMT/Sham recovery phase (“Recovery”, “after rest”).]

2. Myocardial contractility

Changes in impedance cardiography parameters, such as stroke volume (SV) and cardiac output (CO), were used to evaluate the effect of OMT on myocardial contractility. An increase in cardiac output (CO) and stroke volume (SV) would indicate the stimulatory effect of selected OMT on myocardial contractility.

[Time Frame: The responses were measured immediately after the physician finished OMT/Sham (after Manipulations phase) and 10 minutes after post-OMT/Sham recovery phase (“Recovery”, “after rest”).]

3. Blood pressures

Systolic and diastolic blood pressure were measured by sphygmomanometer. A decrease in systolic blood pressure in response to OMT would indicate a decrease in vascular sympathetic tone.

[Time Frame: The blood pressure was measured manually before (before pre-OMT rest) and after the experimental procedure (after "Recovery" phase).]

Eligibility

Minimum Age: 21 Years

Maximum Age: 35 Years

Sex: All

Gender Based: No

Accepts Healthy Volunteers: Yes

Criteria: Inclusion Criteria:

Young adults

- Exclusion Criteria: Any pre-existing chronic cardiovascular diseases,
- Any pre-existing pulmonary diseases,
- Any pre-existing renal diseases,
- diabetes mellitus,
- endocrine disorders affecting the cardiovascular system,
- pregnancy,
- musculoskeletal conditions that can affect the use of the cranial OMTs, or
- acute illness that necessitates consulting a healthcare provider.

Contacts/Locations

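### Blood pressure, a primary outcome, is read only before the pre-treatment rest and after Recovery, so its change includes 10 untreated minutes and it has no immediate response

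*Protocol*

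**What the plan says.** Outcome Measures lists three primary outcomes: heart rate variability (HRV), myocardial contractility (from stroke volume and cardiac output) and blood pressure. The first two have responses both directly after manipulation and after Recovery. For blood pressure the time frame is "The blood pressure was measured manually before (before pre-OMT rest) and after the experimental procedure", and the later reading is placed after Recovery. The Brief Summary agrees: it evaluates blood pressure by "comparing changes in pre- and post- blood pressure readings". Item 3 interprets a fall in systolic pressure in response to OMT as reduced vascular sympathetic tone.

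The Detailed Description sets the timeline as "10 minutes, pre-OMT rest phase (Rest); 8 to 12 minutes (about 10 minutes) of the OMT/Sham (Manipulations"), followed by 10 minutes of Recovery. ECG and impedance run throughout: "Digital data were recorded during the entire experimental protocol".

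The Data analysis paragraph says "Most cardiovascular response variables were measured at baseline, immediately after manipulation" and at the end of the protocol. It continues: "The percent response variables were each analyzed in a three-way analysis of variance (ANOVA) which included time" (two levels, immediate and after rest), treatment (cranial manipulation, sham) and sex.

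On controls, "This study included two control groups; one group received sham manipulations" and the other was not touched. Study Design gives non-randomized allocation and no masking. The Detailed Description adds: "Participants were allowed to participate in multiple experiments (in the experimental and control groups) at least 7 days after the last experiment".

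**The concern.** Three things follow from the placement of the two readings.

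- The baseline precedes the rest phase, so the measured change mixes settling while supine with whatever happens during and after manipulation. A fall within the OMT arm cannot be separated from settling. The comparison with sham removes only the part of settling that the arms share.
- The Protocol looks for an immediate response in the other two primary outcomes but takes no blood pressure reading at that point. An effect that has gone by the end of Recovery leaves no trace. Aim (3) of the Brief Summary, which relates autonomic change to blood pressure change, can be addressed for blood pressure only at the end of the protocol.
- The ANOVA described under Data analysis needs two response times, and blood pressure has one.

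At stake are the reading of a primary outcome and the sympathetic-tone conclusion attached to it.

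**Working it through.** **Interval between readings.** Inputs, all from the Detailed Description: Rest 10 min, Manipulations 8 to 12 min, Recovery 10 min.

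- Shortest: 10 + 8 + 10 = 28 min. Longest: 10 + 12 + 10 = 32 min.
- Share before any manipulation: 10/32 = 31% to 10/28 = 36%.
- The only response is read 10 min after manipulation ends.

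**Bias.** Write the measured change as R + D, where R is the true change during Rest and D is the remaining measured change, cuff error included. The difference in mean change between OMT and sham is

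(mean R in OMT − mean R in sham) + (mean D in OMT − mean D in sham).

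If mean settling is equal, the first bracket is zero. If not, each 1 mmHg of difference in settling moves the comparison by 1 mmHg. The Protocol reports no blood pressure values, so the bracket cannot be given a size. Non-randomized allocation, open-label conduct and return visits mean that equality is not assured by design. They do not show that it fails.

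**Variance.** Let r = SD(R)/SD(D) and let ρ be the correlation of R with D. Relative to an end-of-Rest baseline, the variance of the change is multiplied by

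1 + r² + 2rρ.

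The Protocol gives neither r nor ρ. All values below are assumptions, chosen to show the range:

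| r | ρ | variance ratio |
|---|---|---|
| 0.25 | 0 | 1 + 0.0625 = 1.06 |
| 0.50 | 0 | 1 + 0.25 = 1.25 |
| 0.75 | 0 | 1 + 0.5625 = 1.56 |
| 0.25 | −0.2 | 1 + 0.0625 − 0.10 = 0.96 |
| 0.50 | −0.3 | 1 + 0.25 − 0.30 = 0.95 |

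The ratio falls below 1 whenever ρ < −r/2. A negative ρ is plausible, because people who settle early have less settling left. Even the direction is therefore open.

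**Fit to the planned ANOVA.** Response readings after baseline: HRV 2, stroke volume and cardiac output 2, blood pressure 1. The time factor has 2 levels, so neither the time effect nor any interaction with time can be estimated for blood pressure.

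**The case against.** The strongest reply is that the endpoint is coherent. The Brief Summary and Outcome Measures describe the same pre/post change. Data analysis speaks of most variables, not all, which leaves room for an exception, and a statistical analysis plan that is not shown could name the blood pressure model. This stands in part. A reader might infer that the Protocol contradicts itself on when blood pressure is measured, and it does not. What remains is that the next step applies the time ANOVA to each percent response without naming blood pressure as the exception.

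A second reply is that bias is hypothetical: Rest comes before manipulation and is described identically for everyone, and one blood pressure time frame covers all arms. Nothing says when participants learned their arm, how many came back or in what order. Expectation and familiarity would also act after Rest, where a later baseline would not help. This stands. A reader might infer that the blood pressure comparison is biased, but the document shows only that one protection is missing.

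A third reply is that extra noise is not established. This also stands. A reader might infer lost precision and convert it into a number of participants lost from the 51 enrolled. The ratio can lie on either side of 1. Moreover, 51 covers all three arms, the sizes of which are not given, while the comparison with sham uses only part of them. No such equivalent should be quoted.

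Finally, a manual cuff reading right after manipulation would disturb the participant near the immediate HRV point. That is a fair reason for leaving it out. It does not make an early blood pressure effect observable, and neither control group repairs that.

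**Conclusion.** The point holds as a limitation of minor to moderate weight. Three parts need no assumption. The change in a primary outcome spans 28 to 32 minutes, of which the first 10 are untreated. An effect that fades during Recovery cannot be observed. Blood pressure cannot enter the two-level time ANOVA. A within-arm fall in systolic pressure therefore does not support the sympathetic-tone statement; a difference from sham may, provided settling during Rest was similar in the two arms. The size of any bias and the direction of the effect on variance cannot be determined from the Protocol.

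**What to change.** **For any further data.** Take the existing baseline cuff reading at the end of Rest instead of before it. This needs no extra reading; its small cost is that it must lie outside the Rest window used for HRV and impedance. A reading right after manipulation is optional: it would show an early effect, takes about one minute, and would have to be kept out of the immediate HRV window.

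**For the collected data** (study completed in August 2019):

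- Analyse the single end-of-protocol blood pressure by treatment and sex, without a time factor. Adjust for pre-procedure pressure instead of relying on percent change, and include a participant random effect for people who took part in more than one arm. The adjustment does not remove settling that differs between arms at the same pre-procedure pressure.
- Base the sympathetic-tone statement on the OMT-versus-sham difference, not on within-arm change.
- Limit the correlation of blood pressure with HRV to the end-of-protocol response.
- Reconcile the Brief Summary, Data analysis and Outcome Measures by naming blood pressure as the exception to the time ANOVA.
- State the pre-Rest baseline and the missing immediate reading as limitations.

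The cost is one model and some wording, with no new measurements. The immediate response cannot be recovered.
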